13.1 Tolerability study

The security variables of the use of Zebesten ® will be evaluated in the appointed visits in the chronogram, by means of the following parameters.

1. burning
2. Foreign body sensation
3. Photophobia

13.2 Security evaluation

The security variables of the use of Zebesten ® will be evaluated in the appointed visits in the chronogram, by means of the following parameters.

1. Tear film breakup time
2. Visual capacity
3. Intraocular pressure
4. Epithelial defects
5. Adverse events.

13.3 Efficacy assessment

The efficacy variables of Zebesten® use will be evaluated in the appointed visits in the chronogram, by means of the following parameters:

1. Conjunctival hyperemia
2. OSDI score

Table of scales and variables measurement method

Variable	Unit	Symbol	Type	Measurement method	Normal value
Age	Years	--	Continuous	Calculated as of the date of birth	NA
Gender	Female Male	F/M	Nominal	Direct questioning	NA
Pterygium	Grade 0 Grade I Grade II Grade III Grade IV	--	Ordinal	Direct observation	Grade 0
Adverse events	Number of cases	N	Discreet	Counting	NA
Intraocular pressure	Mercury millimeters	MmHg	Continuous	Goldman applanation tonometry	11-21
Visual capacity	Fraction	Snellen	Nominal	Card	
Tear film breakup time	Seconds	s	Continuous	Direct counting	> 10
OSDI questionnaire	Points	--	Discreet	Questionnaire	
epithelial defects	Grade I Grade II Grade III Grade IV Grade V	--	Discreet	Direct observation with fluorescent staining and lissamine green	Oxford scale

Signs and ophthalmologic symptoms					
conjunctival hyperemia	Very mild Mild Moderate Severe	--	Ordinal	Direct observation. Efron classification.	Normal
burning	Present absent	--	Nominal	Direct questioning	Absent
Foreign body sensation	Present Absent	--	Nominal	Direct questioning	Absent
Photophobia	Present Absent	--	Nominal	Direct questioning	Absent
Prior segment	Normal Abnormal	--	Nominal	Direct observation	Normal

14. PROPOSED STATISTICAL ANALYSIS

The statistical analysis will be performed by a researcher blinded to the intervention groups.

The continuous quantitative variables will be expressed and presented via measures of central tendencies and of dispersion (media, standard deviation and ranges).

The nominal qualitative variables and ordinals will be presented via frequencies and proportions.

The Kolmogorov-Smirnov test will be performed in order to know the normal distribution or not of the obtained results in each study group. Also, the Levene test will be performed in order to know if the variables are the same or different.

Assuming a normal distribution of the data, the intra-group differences will be determined via the t test for paired samples, in the case of the quantitative variables. For the quantitative variables the χ^2 test (chi squared) will be used and in case that the expected frequencies are less than 5 the exact Fisher test will be used.

The differences among the groups will be analyzed via the t test in case of quantitative variables. For the quantitative variables tables of contingency 2x2 will be made and the differences will be calculated via χ^2 (chi squared) with Yates correction in case that the expected frequencies are less than 5 the exact Fisher test will be used).

The level of significance will be alpha of 0.05 or less.

A final statistical analysis will be included to all the subjects that complete 3 visits in the chronogram of activities.

15. Results report

The results obtained during the development of the investigation's protocol will be the responsibility of the sponsor, who is under obligation of reporting them to the pertinent authorities. Plus each one of the participating researchers will receive a results report.

The objective is to achieve the publication of the study on an international magazine with the objective of disseminate the scientific knowledge obtained.

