9. STUDY SCHEDULE

Procedure	SCHEDULE (window periods)				
	Baseline visit	Visit 1	Visit 2	Final visit	Follow-up call
	Day 1	Day 7 (± 2)	Day 15 (± 2)	Day 21 (± 2)	Day 36 (± 2)
Eligibility criteria (inclusion and exclusion)	X				
Pregnancy test (if applicable)	X			X	
Informed consent signature	X				
General and ophthalmic medical record	X				
Ocular symptomatology (A, B, C)	X	X	X	X	
OSDI questionnaire	X	X	X	X	
Subject code assignment	X				
Visual capacity	X	X	X	X	
Previous biomicroscopy (D)	X	X	X	X	
Testing of epithelial defects with fluorescein dye	X	X	X	X	
Testing of epithelial defects with lissamine green dye	X	X	X	X	
Breakup time	X	X	X	X	
PIO measurement	X			X	
Posterior ophthalmoscopy under mydriasis	X			X	
Treatment delivery	X				
Start of drug application	X				
End of drug application				X ¹	
Drug return				X	
Subject diary submission	X				
Subject diary review		X	X	X	
Evaluation of adverse events		X	X	X	X
Evaluation of concomitant drug	X	X	X	X	
Follow-up call					X

9.1 Annotations to Activities Schedule:

- A. Burning
- B. Foreign body sensation
- C. Photophobia
- D. Includes testing of conjunctival hyperemia variable

¹ The application ends one day before to fulfill the 20 days indicated in the treatment.

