10.4 Ocular Symptomology

It refers to the enquiry performed by the researcher for the presence or absence of the following symptoms: burning, foreign body sensation and photophobia, related to pterygium. It must be recorded as present or absent. Symptomology directly related to the administration of the drug product must not be reported in this section. Post-instillation symptoms shall be recorded in the instrument "subject's diary".

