12.4 SAMPLE SIZE CALCULATION

Sample size protocol SOPH155-0415/IV

According to the objectives of the study to evaluate the Zebesten ® effect in subjects with primary pterygium, the variables of primary outcome stipulated in the design were:

- Conjunctival hyperemia
- TRL

Both variables are considered, using similar literature, to perform the calculation of the sample size to meet with the study objectives.

Conjunctival hyperemia

The sample size was calculated according to the formula for the continuous quantitative variables:

$$n = 2 \frac{(Z_{\alpha/2} - Z_{\beta})(\delta)}{d^2}$$

With a statistical trust of 95% that corresponds to the type I error, and is the same as 1.96, with a potency of 80% that corresponds to the type II error, and equals to 0.84. It is considered as a standard deviation for the increase of 0.4 degrees of severity1 in the scale of conjunctival hyperemia after a pterygium surgery, with an expected difference of at least 2.9 degrees of severity.

Based on the previous the result was 69 cases (eyes) per group, which was incremented 20% by consideration of the losses (14 subjects), with **a total of 83 cases per group**, with a total population of study of **166 eyes to treat**.⁸

Tear film breakup time

The sample size was calculated according to the formula for continuous quantitative variables:

$$n = 2 \frac{(Z \propto -Z_1 - \beta)(\delta)}{d^2}$$

With a statistical trust of 95% that corresponds to the type I error, and is the same as 1.96, with a potency of 80% that corresponds to the type II error, and equals to 0.84. It's considered as a standard deviation for the increase of 1.47 seconds 2 in the tear film breakup time posterior to 60 days of ciclosporin application A, with an expected difference of at least 10.2 seconds.

Based on the previous the result was of 120 cases per group, which was incremented 20% per consideration to the losses (24 cases), with a total of **144 cases per group**, with a total population of study of **288 eyes to treat**.

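### Section 14 names an unpaired test (chi-squared or Fisher) for within-group change in symptoms recorded present/absent in the same cases at several visits

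*Combined protocol and SAP*

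**What the plan says.** Section 14 treats within-group and between-group comparisons in separate paragraphs. Within groups, "the intra-group differences will be determined via the t test for paired samples, in the case of the quantitative variables". The next sentence gives the rule for a second class of variables: the "test (chi squared) will be used and in case that the expected frequencies are less than 5 the exact Fisher test will be used". That class is also printed as quantitative. It must mean qualitative: the two classes cannot be the same, the same slip recurs in the next paragraph, and expected frequencies belong to categorical tables.

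The next paragraph turns to the arms: "The differences among the groups will be analyzed via the t test in case of quantitative variables". It then gives 2x2 tables with chi-squared (Yates) or Fisher for the other variables. The threshold is set once: "The level of significance will be alpha of 0.05 or less".

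On the symptoms, section 10.4 says "It must be recorded as present or absent". The schedule in section 9 marks them at baseline, visits 1 and 2 and the final visit. Section 13.1 makes burning, foreign body sensation and photophobia the tolerability parameters, and sections 6 and 13 list them as secondary outcomes. No paired test for categorical data appears anywhere in the document.

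**The concern.** The paired t test shows that the authors treat visits as paired for quantitative variables. For the symptoms the pairing is dropped, and the sentence can be carried out in two ways.

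- **Visit by symptom.** Each case enters twice, as if the two visits were different people. Correlation between visits is ignored.
- **Baseline by follow-up.** The test asks whether status at one visit predicts status at the other. That is association, not change.

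Neither tests whether symptoms changed within cases. The first can miss real change, including worsening in the variables that carry the tolerability assessment. The second can report significance when the proportion with the symptom has not moved.

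**Working it through.** The plan states no sample size, power or p-value for within-group symptom change, so there is no figure of its own to reproduce. The check is on the behaviour of the named test.

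**Inputs from the document.** Alpha is 0.05 (section 14; sidedness not stated, two-sided taken). Section 12.4 reports that "the result was 69 cases (eyes) per group", raised for losses to "a total of 83 cases per group". Section 7.2 counts each eligible eye of a bilateral subject as one case.

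**Assumptions, not in the document.** 69 evaluable cases per arm for symptoms; prevalence 60%; phi, the correlation between two visits of one case, from 0 to 0.7.

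**Visit by symptom, no change.** With prevalence p at both visits, the chi-squared test uses variance 2p(1−p)/n for the difference in proportions. The true variance is 2p(1−p)(1−phi)/n. The rejection rate is therefore about 2[1 − Φ(1.96/√(1−phi))]:

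- phi 0.3: 1.96/0.837 = 2.34, giving 1.9%
- phi 0.5: 1.96/0.707 = 2.77, giving 0.6%
- phi 0.7: 1.96/0.548 = 3.58, giving 0.03%

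**Visit by symptom, true fall from 60% to 45%.** The average proportion is 0.525. The test's standard error is √(2 × 0.525 × 0.475/69) = 0.0850, so it needs a difference of 1.96 × 0.0850 = 0.1666. At phi 0.5 the true standard error is √[(0.24 + 0.2475 − 2 × 0.5 × √(0.24 × 0.2475))/69] = 0.0594. Power is about P(Z > (0.1666 − 0.15)/0.0594) = P(Z > 0.28) = 39%.

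**Cross-table, no change.** The noncentrality is n × phi². At phi 0.3 it is 69 × 0.09 = 6.21, with square root 2.49, so the test rejects about Φ(2.49 − 1.96) = 70% of the time. At phi 0.5 it is 17.25, giving about 99%.

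**Simulation** (n = 69, uncorrected chi-squared, asymptotic McNemar) agrees:

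| phi | Visit by symptom, no change | Cross-table, no change | Power, visit by symptom | Power, McNemar |
|---|---|---|---|---|
| 0 | 4.6–4.7% | 5% | 42% | 42% |
| 0.3 | 1.8% | 71% | 41% | 57% |
| 0.5 | 0.5–0.6% | 99% | 39% | 71% |
| 0.7 | below 0.1% | about 100% | 35% | 94% |

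With no change, McNemar rejected between 4.3% and 5.4% of the time in all settings run.

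**Two constructed tables.**

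1. Of 83 cases, 50 have the symptom at baseline and 38 at the end (14 resolved, 2 new). Visit by symptom: chi-squared = 166 × (50 × 45 − 33 × 38)²/(83 × 83 × 88 × 78) = 3.48, p = 0.062 (Fisher 0.087). Exact McNemar on 2 of 16 discordant pairs: p = 2 × (1 + 16 + 120)/65,536 = 0.004.
2. Of 69 cases, 30 are present at both visits, 10 resolve, 10 are new and 19 are absent at both. The count is 40 at each visit, so nothing changed overall, and McNemar's statistic is (10 − 10)²/20 = 0. The cross-table chi-squared is 69 × (30 × 19 − 10 × 10)²/(40 × 29 × 40 × 29) = 11.33, p = 0.0008.

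**The case against.** The strongest reply is that little depends on these tests. The trial is randomised and placebo-controlled, the treatment comparison sits in the between-group paragraph, and no success criterion or sample size uses a within-group symptom p-value. Frequencies will be tabulated anyway, so marked worsening would still be seen. All of this stands and limits the scope of the point. It does not make the named test suitable.

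A second reply is that the size depends on a correlation and a prevalence that the document does not give. That also stands. A reader might infer that the visit-by-symptom test is always far too conservative, or that the cross-table test is significant almost always. Neither follows. At phi 0 the unpaired test and McNemar's test agree. At phi 0.2 the power loss is modest (41% against 51%), and the cross-table test rejects 39% of the time under no change. Negative correlation would make the visit-by-symptom p-values too small (about 7.5% rejection at phi −0.2), although positive correlation is what one expects when the same person is asked again days later.

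A third reply is that McNemar's test alone is not enough, because the cases are eyes. This is right and changes the remedy. Suppose symptoms agree in both eyes and 14 of the persons behind 69 cases are bilateral (an assumption). The variance of the net change then rises by (69 + 2 × 14)/69 = 1.41, and an unclustered McNemar test rejects about 2[1 − Φ(1.96/√1.41)] = 10% of the time under no change. With 20 bilateral persons it is about 12%.

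Finally, the reading of the misprinted class is an inference, but no other reading makes the sentence usable.

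**Conclusion.** The point holds in a limited form. As written, section 14 assigns an unpaired test to paired present/absent data, and that defect does not depend on any assumed number. On the visit-by-symptom reading the p-values are too large whenever phi is positive. On the cross-table reading they answer a different question. The percentages rest on the assumed 69 cases per arm, 60% prevalence and the phi shown, and should be read as a range.

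The reach is the within-group tests of the three secondary/tolerability symptoms. It extends to conjunctival hyperemia, a primary outcome that the section 13.3 table types as ordinal, only if hyperemia is analysed under the same rule; section 14 does not say. A reader might infer that the comparison of bromfenac with placebo is compromised. The document does not support that, because the between-arm test is specified separately and this error does not enter it.

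**What to change.** Amend section 14 as follows.

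- Correct quantitative to qualitative for the class tested by chi-squared or Fisher.
- Name the contrast for within-group change: baseline to final visit.
- Use McNemar's test for present/absent symptoms, in its exact form when discordant pairs are few, and the Wilcoxon signed-rank test for ordinal grades such as conjunctival hyperemia.
- Report the paired change with a 95% confidence interval.
- Where both eyes of a subject are included, use a subject-clustered version, for example GEE with subject as the cluster.
- Restrict chi-squared and Fisher to comparisons between arms.

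The cost is a few sentences in section 14 and slightly more programming for the clustered analysis. No visits, measurements or subjects are added.

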7.5 Distribution into treatment groups

The subjects are distributed into the study groups on the visit indicated in the study timetable, through simple 1:1 randomization, closed envelope technique, through a specialized software that uses random number tables to achieve a uniform distribution in each of the treatment groups.

[figure not shown]

Fig. 1. DISTRIBUTION OF STUDY SUBJECTS. Shows the randomized distribution of the study subjects in the research protocol using a computing system through the closed envelope technique.

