10.3.2.2.1 Tear Film Breakup Time

It will be measured after blinking once and the patient will be asked to not blink again until the tear film breaks on the cornea. If it is more than 10" it will be regarded as normal. The whole number value will be recorded on the FRC.

Example:

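### The between-arm t test has no baseline covariate, although breakup time, OSDI, acuity and IOP are all measured at baseline: valid, but inefficient

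*Combined protocol and SAP*

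**What the plan says.** Section 14 (Proposed statistical analysis) covers between-arm comparisons of quantitative variables in one sentence: "The differences among the groups will be analyzed via the t test in case of quantitative variables". No covariate, ANCOVA or mixed model is named. The sentence does not say whether the test is run on the visit value or on the change from baseline, nor at which visit. Baseline values enter only within each arm, where "the intra-group differences will be determined via the t test for paired samples, in the case of the quantitative variables". That comparison does not contrast the treatments.

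The schedule in section 9 has breakup time, OSDI and visual capacity at baseline and at all three later visits, and IOP at baseline and the final visit. Breakup time is numeric (section 10.3.2.2.1: "The whole number value will be recorded on the FRC"), and section 10.3.1 converts acuity to LogMAR for statistical use.

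Breakup time is listed as a primary outcome in sections 6 and 13. OSDI is one of two efficacy variables in section 13.3. Allocation is "through simple 1:1 randomization, closed envelope technique" (section 7.5), with no stratification described. Section 7.2 lets both eyes of a subject enter as separate cases.

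**The concern.** A baseline measurement of the same variable usually explains part of the follow-up variance. A two-sample t test on visit values leaves that variance in the error term, so the confidence interval is wider than it need be. It also leaves any chance baseline difference between arms in the point estimate. A t test on change uses baseline with a fixed coefficient of 1, which over-corrects when the correlation is weak.

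What is at stake is precision, chiefly for breakup time. Section 12.4 states 120 per group before losses for that outcome, but the trial is sized at 83 per group, from the hyperemia calculation. Precision is therefore lost on a primary outcome that is already short of its own stated size.

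**Working it through.** **Inputs from the documents**
- Alpha: "The level of significance will be alpha of 0.05 or less" (section 14). Two-sided z: "With a statistical trust of 95% that corresponds to the type I error, and is the same as 1.96" (section 12.4).
- Power: "with a potency of 80% that corresponds to the type II error, and equals to 0.84" (section 12.4).
- Breakup time: SD 1.47 s, difference 10.2 s, 120 per group before losses and 144 after (section 12.4).
- Enrolment: 166 cases, 83 per group, that is 69 plus 14 for losses (sections 7.2 and 12.4).

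**Assumed:** the correlation ρ between baseline and follow-up, 0.3 to 0.7; cases independent.

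**1. The plan's own 120.** The standard formula gives n = 2 × (1.96 + 0.84)² × 1.47² / 10.2² = 2 × 7.84 × 2.161 / 104.04 = 0.33, that is 1 per group, not 120. A value near 120 appears only if SD and difference are swapped and the z values are subtracted: 2 × (1.96 − 0.84)² × 10.2² / 1.47² = 120.8. The literal inputs therefore cannot anchor a power calculation. I take the stated 120 per group as the intended size and work back to the effect it implies.

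**2. Implied effect.** d = √2 × (1.960 + 0.842) / √120 = 0.362 SD.

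**3. Residual SD factor k for each analysis**
- t test on visit values: k = 1
- t test on change: k = √(2(1 − ρ))
- ANCOVA: k = √(1 − ρ²)

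The ratio of the ANCOVA variance to the change-score variance is (1 − ρ²) / (2(1 − ρ)) = (1 + ρ)/2, which never exceeds 1. The change score beats no adjustment only if 2(1 − ρ) < 1, that is ρ > 0.5.

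**4. Power with 69 evaluable eyes per group.** Power = Φ(d√(n/2)/k − 1.96), with d√(69/2) = 0.3617 × 5.874 = 2.124.

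| ρ | t test, visit value | t test, change | ANCOVA |
|---|---|---|---|
| 0.3 | 56.5% | 43.5% | 60.5% |
| 0.5 | 56.5% | 56.5% | 68.9% |
| 0.7 | 56.5% | 78.3% | 84.5% |

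Example at ρ = 0.5: 2.124 / 0.866 − 1.96 = 0.493, and Φ(0.493) = 0.689.

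With all 83 per group evaluable, the visit-value t test has 64.4% power, and ANCOVA has 68.5%, 76.7% and 90.4%.

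**5. Eyes per group for 80% power at this effect.** Visit-value t test: 120. ANCOVA, 120(1 − ρ²): 109.2, 90.0 and 61.2. Change, 240(1 − ρ): 168, 120 and 72.

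**6. Chance imbalance.** The standard error of the baseline difference at 69 per group is √(2/69) = 0.170 SD. A visit-value t test carries ρ times the realised difference into the estimate: at ρ = 0.5 and a difference of one standard error, 0.5 × 0.170 = 0.085 SD. A change-score test carries (ρ − 1) times it. ANCOVA carries none, to first order.

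**The case against.** The strongest reply is that nothing here is an error. Under randomisation the two-sample t test is unbiased and controls type I error without a baseline term, and chance imbalance is random error that its standard error already covers. That stands. A reader might infer that the planned test is biased, or that simple randomisation makes it unsafe; the documents support neither. Blocking would not balance breakup time or OSDI unless it were stratified on them.

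Second, the size of the loss cannot be read from the documents. At ρ = 0.3 the gain is 4 points (60.5 − 56.5). That also stands: the direction is certain for any non-zero correlation, but the amount is not.

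Third, the t test may be meant for change. Section 12.4 uses wording such as "It is considered as a standard deviation for the increase of 0.4 degrees of severity1 in the scale of conjunctival hyperemia", with a like phrase for breakup time. A change score does use baseline, so only the absence of a covariate is certain. This does not rescue the plan, because change is never more precise than ANCOVA.

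Fourth, it is tempting to start from 80% power at 69 per group (0.477 SD) and quote 84%, 90% and 97.5% for ANCOVA. But section 12.4 derives 69 for hyperemia, which section 13.3 types as ordinal and this point leaves aside. Breakup time's own figure is 120. OSDI, IOP and acuity have no sizing at all.

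Fifth, section 13.2 also classes breakup time, acuity and IOP as safety variables. For IOP and acuity, power to show a difference is a weak argument; a narrower interval is the benefit.

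**Conclusion.** The point holds as one of efficiency. The planned between-arm t test is valid, but it leaves out a covariate that the trial already collects for breakup time, OSDI, acuity and IOP. On breakup time's own stated size, with 69 evaluable eyes per group, adjustment raises power from about 56.5% to between 60.5% and 84.5% over assumed correlations of 0.3 to 0.7.

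These figures rest on the assumed correlation, on the effect worked back from 120 per group, on a normal approximation, and on treating eyes as independent. With two eyes from some subjects the absolute power figures will differ.

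It should not be read as covering every outcome. Adverse events, also listed as primary, have no baseline entry in the schedule. Nor should 10.2 s with SD 1.47 s be taken to show that power is near 100% under any analysis, since those inputs do not reproduce the stated 120.

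**What to change.** In section 14, replace the between-group t test for breakup time, OSDI, IOP and LogMAR acuity with a linear model: value at the final visit = treatment + baseline value of the same variable. Report the adjusted difference with its 95% CI. For the eye-level variables (breakup time, IOP, acuity), account for two eyes of one subject by a random subject effect or cluster-robust standard errors. Analyse OSDI once per subject, because the questionnaire in Appendix 3 gives one score per person. Fix this wording before unblinding; it also settles the visit and the choice between visit value and change, both now left open.

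The cost is slightly more analysis work and a model that must handle paired eyes. No visit, measurement or case report form field changes.

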5. PURPOSES

5.1 General purpose:

Evaluate the efficacy and safety of Zebesten ® (bromfenac 0.09 %) ophthalmic solution in the treatment of conjunctival hyperemia and ocular surface inflammation in a clinical grade I to III Pterygium model.

5.1.1 Specific purpose 1:

Evaluate the efficacy of Zebesten ® in the control of conjunctival hyperemia in subjects with Pterygium through its qualitative assessment through the validated analogous scale of the cornea unit and contact lenses of the University of South Wales.⁵

5.1.2 Specific objective 2:

Evaluate the safety of Zebesten ® through the evaluation of the corneal and conjunctival epithelium through fluorescein and lissamine green staining, the measurement of intraocular pressure, and the Tear film breakup time.

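### Section 14 gives conjunctival hyperemia, a primary outcome, no unambiguous or suitable between-arm test

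*Combined protocol and SAP*

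**What the plan says.** Sections 6 and 13 list conjunctival hyperemia among the primary outcomes, and section 13.3 names it as one of two efficacy variables.

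- **Sizing.** Section 12.4 uses a formula for continuous quantitative variables, with SD 0.4, an expected difference of 2.9 grades, 95% confidence and 80% power. It reports 69 eyes per group, raised by 20% to 83.
- **Type and scale.** The table in section 13.3 types hyperemia as ordinal, with levels "Very mild Mild Moderate Severe" and method "Direct observation. Efron classification". Its normal value is Normal, which is not a listed level. Section 5.1.1 says it will be assessed "through the validated analogous scale of the cornea unit and contact lenses of the University of South Wales".
- **Description.** In section 14: "The nominal qualitative variables and ordinals will be presented via frequencies and proportions". Ordinal variables are not mentioned there again.
- **Within arms.** Section 14 gives a paired t test, assuming normality. It continues: "For the quantitative variables the χ^2 test (chi squared) will be used", with Fisher for small expected counts.
- **Between arms.** "The differences among the groups will be analyzed via the t test in case of quantitative variables". The next sentence reads "For the quantitative variables tables of contingency 2x2 will be made and the differences will be calculated via" chi-squared with Yates correction, or Fisher.
- **Normality.** Kolmogorov-Smirnov is to be run in each study group. No alternative is named if it rejects.
- **Visit.** Section 14 names no visit for the comparison. Its only reference to visits is the completeness rule: "A final statistical analysis will be included to all the subjects that complete 3 visits in the chronogram of activities".

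**The concern.** Section 14 assigns both kinds of test to *quantitative* variables and never links hyperemia to either. Two analyses of a primary outcome are therefore open, and they can give different answers. Both have a defect of their own: the 2x2 test depends on an unstated cut, and the t test sits behind a normality check with no way forward if it fails.

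The decision can be taken after the data are seen. Blinding the analyst to arm, as section 14 provides, limits steering toward one arm. It does not prevent trying several tests or cuts until one gives a small p-value.

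**Working it through.** **1. The plan's own figure.** The inputs are all from section 12.4: z-values 1.96 and 0.84, SD 0.4, difference 2.9.

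- Standard two-means formula: 2 × (1.96 + 0.84)² × 0.4² / 2.9² = 2 × 7.84 × 0.16 / 8.41 = 0.30, so 1 eye per group.
- Formula as printed (minus sign, no squares): 2 × 1.12 × 0.4 / 8.41 = 0.11.
- SD and difference swapped in the standard formula: about 825 per group.

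None gives 69, so the stated inputs cannot show how sensitive the trial is to the choice of test. Working back from 69 at 80% power, the detectable difference is √(2 × 7.84 / 69) = 0.477 SD. I use this as the central scenario.

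**2. The two readings.**

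- *Reading A (likely).* The second *quantitative* in each paragraph means qualitative. Section 14 describes ordinals together with nominal variables, so hyperemia goes to the 2x2 test. Four grades allow three cuts, and none is named. Within arms, chi-squared or Fisher would compare baseline and later grades of the same eyes as if they were separate samples.
- *Reading B.* Hyperemia is treated as a score, as section 12.4 implies, and goes to the t test. Normality is checked first. The assumption is written in the within-arm sentence and not repeated for the between-arm t test, but no other role is given to the check.

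**3. The normality check on four grades.** The empirical distribution jumps at each grade by the share of eyes in it. A fitted normal curve is continuous, so the largest gap is at least half the biggest jump. With four grades the biggest share is at least 1/4, so the Kolmogorov-Smirnov statistic is at least 0.125 whatever the data. In 2,000 simulated samples of 69 eyes for each of two sets of grade proportions, with mean and SD estimated from the sample, the test rejected normality in 100%.

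**4. Between-arm power.** Assumptions: a latent normal variable cut into four grades; control cumulative proportions of 25/50/75% or 10/40/80%; 69 independent eyes per arm; two-sided 0.05; shift toward lower grades; Yates, or Fisher if an expected count is below 5; 8,000 runs. Ranges span the three cuts and both sets of proportions.

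| True shift | 2x2 test | t test or Wilcoxon |
|---|---|---|
| 0.3 SD | 14-23% | 36-38% |
| 0.477 SD | 34-53% | 73-74% |
| 0.7 SD | 60-87% | 96-97% |

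At 0.477 SD the t test and the 2x2 test disagree on significance in 23-43% of trials, depending on the cut. A different model (proportional odds ratio 2.4, 69 per arm) points the same way: 80-81% for the t test against 33-65% for the 2x2 test.

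**5. False positives if the choice is made late.** With no true difference (20,000 runs), a single pre-named cut rejects in 2.6-3.2% and the t test in 4.9-5.0%. The best of three cuts rejects in about 8% (7.8-7.9%). The best of the t test or any cut rejects in about 9-10% (8.9-9.6%).

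**The case against.** **Ordinals do have a test.** A reader might infer that section 14 assigns ordinal variables no test at all. The documents do not support that. The text is a rough translation, and once *quantitative* is read as *qualitative*, ordinals fall naturally under chi-squared or Fisher. What remains is narrower: the assignment is not stated, it conflicts with the sizing, and a 2x2 table of four grades cannot be built from the plan.

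**At the plan's effect size the choice is harmless.** At 2.9/0.4 = 7.25 SD every test would reject. That is true, but those inputs give 1 eye per group, not 69. On four grades scored 1 to 4, a difference of 2.9 is 2.9/3 = 97% of the possible range (2.9/4 = 72.5% if Normal is a fifth level).

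**The loss of power could be made to look larger.** If shifts toward worse hyperemia are included, 2x2 power at 0.477 SD falls as low as 17%. The stated purpose is control of hyperemia, so only shifts toward lower grades are used here.

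**The scale is not wholly unsettled.** Sections 10.3.2 and 13.3 list essentially the same four levels. The conflict is in the scale's name between sections 5.1.1 and 13.3. The normal-value column is filled loosely (for epithelial defects it holds the name of a scale), so Normal is weak evidence of a fifth level.

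**Naming a linear model is not enough.** This objection stands in full. Unless the plan also says that Kolmogorov-Smirnov does not decide the test, the question reopens at analysis.

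**Conclusion.** The point holds: section 14 should be changed, although the data would remain analysable. A primary outcome has two possible between-arm tests, neither usable as written without a further decision that the plan does not make.

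At the effect that 69 eyes per arm implies, the 2x2 route gives 34-53% power against 73-74% for a test using all grades. Selecting among cuts or tests after the fact roughly doubles the nominal 5% error at worst. These sizes are illustrative. They rest on assumed grade distributions, effects and cuts and on independent eyes. The failure of the normality check does not depend on the treatment effect, because it follows from having only four grades.

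The within-arm use of unpaired tests on the same eyes is a real but minor fault, since those tests do not answer the randomised question.

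**What to change.** In section 14:

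1. Name one between-arm analysis of hyperemia at a named visit that uses all grades: a linear model on grade scores or a proportional-odds model. Their power is nearly equal in simulation (both 81% at 0.477 SD with baseline grade included and one eye per subject). Include baseline grade as a covariate, which is a gain in precision, and subject as cluster where both eyes enter under section 7.2.
2. State that the Kolmogorov-Smirnov result does not decide the test.
3. Keep any 2x2 proportion descriptive, with its cut named in advance.
4. Correct the *quantitative* wording, and say which variables each test sentence covers.
5. Within arms, use paired tests as supportive analyses only.

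Elsewhere, reconcile the scale name in sections 5.1.1 and 13.3, say whether Normal is a level, and restate the sample-size basis in section 12.4 to match the chosen analysis.

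**Cost.** Wording only; no new visits or measurements. Clustering can cost some power. If 30% of subjects contribute both eyes to the same arm, with between-eye correlation 0.5 (all assumed), power at 0.477 SD falls from about 79% unclustered to about 74%. The unclustered figure comes with a false-positive rate of about 6.5%, so part of that apparent power is not real. If fellow eyes are split between arms, there is no loss.
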